#### Time to Progression

Time to improvement is the time in which the patient sees an increase after first study treatment in the WHO 7-point ordinal scale from baseline to a value at least one level higher in days (*date of increase in WHO scale - first dose date + 1*). In the case that a patient has not increased in the WHO scale at time of analysis or withdraws from the study before leaving the hospital, they will be censored at their date of last assessment in the data cut or early discontinuation date, respectively.

Time to progression will be analyzed using the Kaplan-Meier methods as described in the above time to event analyses.

#### Change from baseline in respiratory outcomes

Respiratory outcomes include the secondary endpoint of SpO2 and the exploratory endpoint **CCI**

Standard descriptive statistics (mean, standard deviation, median, minimum, maximum) will be used to summarize each outcome and its change from baseline by treatment group at Day 10. Only scheduled visits as described in the schedule of assessments (Section 1.3 of protocol) will be included for each endpoint.

Patients who showed an increase 2% or higher in SpO2 from baseline at Day 7 will be flagged and summarized. Patients who have a reduction in SpO2 to < 90% will be flagged and summarized.

In addition, the least square means and least square mean difference (RESP301 + SOC – SOC Alone) along with their respective 95% CIs and p-values will be presented. Least square means and mean difference will be estimated using a Mixed Model with Repeated Measurements (MMRP) /Analysis of Covariance (ANCOVA) with the treatment, patient's country and risk group as randomized and visit as the model terms, and baseline value as the covariate and change from baseline as the dependent variable. Patients will be included as a random effect and an unstructured covariance structure will be specified in the initial model. If the model fails to converge alternative covariance structures will be applied in the following order: heterogenous compound symmetry, compound symmetry.

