### 3.3 Endpoints

#### 3.3.1 Efficacy Variables

Primary:

- Proportion of participants who progress to level >4 of modified WHO ordinal scale due to COVID-19 by Day 14

Key Secondary:

- Change in room air SpO2 from baseline over time
- Change in NEWS 2 symptom score from baseline over time
- Change from baseline on the modified WHO ordinal scale at each visit up to Day 28
- Time to improvement to at least one level lower of the modified WHO ordinal scale
- Time to progression to at least one level higher of the modified WHO ordinal scale

Additional Secondary:

- Time to hospital discharge
- Incidence of mortality by Day 28

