### 4.2 General Presentation Considerations

Baseline is the last available pre-treatment assessment. All assessments should have time collected. If time is not collected and date of assessment is the same as the *first dose date*, then assessment will be assumed to be collected prior to treatment unless schedule of assessments and protocol indicate planned collection is always after dosing.

Day-of-Discharge (DoD) is the day when patient is discharged from the hospital.

Durations are calculated as the stop date minus the start date plus one.

For elapsed time (e.g. time since the initial diagnosis), if the reference date is on or after the event date, then the elapsed time is the reference date minus the event date plus one. If the reference date is before the event date, then the elapsed time is the reference date minus the event date.

If more than one laboratory value is available for a given study day, the first valid observation will be used in summaries and all observations will be presented in listings. If it is not possible to determine which is the first measurement due to missing times, then the average of all measurements for that time point will be used as the value for that time point.

Continuous data will be summarized in terms of the mean, standard deviation (SD), median, minimum, maximum and number of observations, unless otherwise stated. Continuous data that are expected to be skewed will be presented in terms of the maximum, upper quartile, median, lower quartile, minimum and number of observations. The minimum and maximum will be reported to the same number of decimal places as the raw data recorded in the database. The mean, median, lower quartile and upper quartile will be reported to one more decimal place than the raw data recorded in the database. The SD will be reported to two more decimal places than the raw

---

data recorded in the database. In general, the maximum number of decimal places reported shall be four for any summary statistic.

The mixed model with repeated measurements /analysis of covariance model with treatment, country, participant's clinical status at Baseline and visit as the model term, and Baseline value as the covariate will be used to test for the significance of the treatment difference. Least square means, standard errors, 95% CIs and p-values will be presented.

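### The SpO2 repeated-measures model has no treatment-by-visit term, pairs a patient random effect with an unstructured covariance, and carries two different covariate lists

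*SAP*

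**What the plan says.** All the text below is from version 2.0 of the SAP.

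- **Endpoint.** Section 3.3.1 lists as key secondary "Change in room air SpO 2 from baseline over time".
- **Endpoint-specific model.** Section 4.9.3, under respiratory outcomes, models change from baseline by a mixed model for repeated measures or an ANCOVA, without saying which, "with the treatment, patient's country and risk group as randomized and visit as the model terms, and baseline value as the covariate". Least square means, their difference, 95% CIs and p-values are to be presented. No visit is named for the difference.
- **Covariance.** The same paragraph states: "Patients will be included as a random effect and an unstructured covariance structure will be specified in the initial model". It continues: "If the model fails to converge alternative covariance structures will be applied in the following order: heterogenous compound symmetry, compound symmetry".
- **Descriptive part.** Descriptive statistics in that section "summarize each outcome and its change from baseline by treatment group at Day 10".
- **General model.** Section 4.2 gives a mixed model or ANCOVA for testing the treatment difference, with "treatment, country, participant's clinical status at Baseline and visit as the model term, and Baseline value as the covariate".
- **Randomization factors.** Section 3.1 stratifies by country and by risk-factor category (none, one, two or more). Baseline clinical status is not a stratum.

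**The concern.** There are three separate problems with one model.

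1. **No treatment-by-visit term.** Visit enters only as a main effect, so the treatment difference is forced to be the same at every visit. An endpoint framed as change over time invites the question of when a difference appears and how large it is at a given day. The specified model cannot answer that.
2. **A redundant random effect.** An unstructured within-patient covariance already contains every variance and covariance between visits. A patient random intercept on top adds a parameter that the data cannot separate from it. The plan makes non-convergence the trigger for moving to simpler structures, so a fault in the specification could move the analysis off the unstructured covariance.
3. **Two covariate lists.** Section 4.2 has baseline clinical status where section 4.9.3 has risk group as randomized. Two programmers working from the same SAP could fit different models to a key secondary endpoint of an open-label trial.

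**Working it through.** The SAP states no power or sample size for this model, so there is no figure of its own to reproduce. The number of visits, *p*, is in the protocol's schedule, which is not at hand; values from 3 to 10 are assumed.

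**Step 1. What the treatment coefficient estimates.** With treatment and visit as main effects only, the model has one coefficient for treatment. With complete data it estimates a weighted average of the visit-specific differences. If the true difference at visit *k* is *k/p* (linear growth to 1 at the last visit) and all visits weigh equally, as under compound symmetry, the coefficient is

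(1/*p*) × Σ *k/p* = (*p* + 1) / (2*p*).

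- *p* = 3: 4/6 = 0.67
- *p* = 5: 6/10 = 0.60
- *p* = 10: 11/20 = 0.55

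A first-order autoregressive correlation of 0.8 gives the same values. If the true difference is the same at all visits, the coefficient equals it and nothing is diluted.

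**Step 2. The same with patients leaving.** Assume 10 visits, 10% of the remaining patients lost after each visit equally in both arms, compound symmetry and a within-patient correlation of 0.5. A patient with *k* visits has weight 2*k*/(*k* + 1) and mean effect (*k* + 1)/20, whose product is *k*/10. The fraction with exactly *k* visits is 0.1 × 0.9^(*k*−1) for *k* = 1 to 9, and 0.9^9 = 0.387 for *k* = 10.

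- Numerator: mean number of visits / 10 = [(1 − 0.9^10)/0.1]/10 = 6.513/10 = 0.651
- Denominator: Σ (fraction) × 2*k*/(*k* + 1) = 1.629
- Ratio: 0.651/1.629 = 0.40

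Every input of this step is an assumption.

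**Step 3. Identifiability of the covariance.** The marginal covariance is V = R + σ_b² J, where J is the matrix of ones and σ_b² the random-intercept variance. For an unstructured R, replacing (R, σ_b²) by (R + cJ, σ_b² − c) leaves V unchanged, so one parameter is free. For compound symmetry, V = σ² I + (τ + σ_b²) J, and only the sum τ + σ_b² can be estimated. Parameter counts against the numerical rank of the derivative of V:

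| R, plus random intercept | 3 visits | 5 visits | 10 visits |
|---|---|---|---|
| Unstructured | 7, rank 6 | 16, rank 15 | 56, rank 55 |
| Heterogeneous CS, visit SDs unequal | 5, rank 5 | 7, rank 7 | 12, rank 12 |
| Heterogeneous CS, visit SDs equal | 5, rank 4 | 7, rank 6 | 12, rank 11 |
| CS | 3, rank 2 | 3, rank 2 | 3, rank 2 |

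The initial model and the last fallback are each one parameter too many. The first fallback is identifiable when the visit variances differ.

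**Step 4. The two lists side by side.** Both contain treatment, country, visit and baseline value. They differ in one term: baseline clinical status (4.2) against "country and risk group as randomized and visit as the model terms" (4.9.3). Only risk group matches section 3.1. Neither section refers to the other.

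**The case against.** The strongest reply is that a single visit-averaged difference is a legitimate, if less informative, summary of change over time. The SAP does not declare Day 10 as the target of the model: in section 4.9.3 Day 10 belongs to the descriptive statistics, and the Day 10 rule at the first interim analysis is a responder comparison that does not use this model. This stands. The pooled coefficient is not a biased Day 10 estimate. What remains is that the plan offers no visit-specific estimate at all.

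On the covariance, the patient random effect may only be loose wording for naming the patient as the subject of the repeated measures. And even when fitted literally with an unstructured matrix, it does not change the set of marginal covariances, so a converged fit gives the same treatment estimate. Both points are fair; they reduce the harm to a possible convergence nuisance.

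On the covariates, an endpoint-specific section would ordinarily govern over general presentation rules. That is plausible, but the SAP does not say so.

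A reader might infer three stronger things that the document does not support:

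- **That about half of the treatment effect is lost.** This needs an assumed linear effect, visit schedule and discharge pattern, none of which the SAP gives.
- **That the fallback sequence cannot cure the redundancy.** Its first step, heterogeneous compound symmetry, can do so when visit variances differ.
- **That NEWS 2 has no inferential analysis.** Its own section is descriptive, but it is also key secondary ("Change in NEWS 2 symptom score from baseline over time"), and the general model in section 4.2 is not confined to SpO2, so it can be read as covering NEWS 2.

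**Conclusion.** The point holds as a specification fault in a key secondary analysis. Three things rest on the text and algebra alone: both term lists omit treatment-by-visit, so no per-visit or Day 10 contrast is available; the initial model and the last fallback are over-parameterised by exactly one parameter; and the two lists differ by one term with no stated precedence.

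The size of any dilution is not established. The figures of 0.55 to 0.67 (complete data) and 0.40 (10% loss per visit) show what could happen if the effect grew linearly; under a constant effect the figure is 1. The redundancy risks an unnecessary move to a simpler covariance, not bias in a converged fit.

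The primary CMH test is untouched, and the multiplicity section (4.9.1.4) sets no alpha control for secondary endpoints. The correction is nevertheless worth making, because it changes what the key secondary analysis can estimate.

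**What to change.** Specify one mixed model for repeated measures, in place of the open choice between a mixed model and ANCOVA:

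- Fixed effects: treatment, visit, treatment-by-visit, baseline value, country, and risk group as randomized.
- Unstructured within-patient covariance, with no patient random effect, at the initial step and at each fallback.
- Per-visit treatment differences, including Day 10, with 95% CIs, alongside any visit-averaged difference. State which of these is the main summary.
- The same term list in sections 4.2 and 4.9.3, or a sentence in 4.2 that endpoint-specific sections take precedence.

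The cost is SAP wording and *p* − 1 more fixed-effect parameters (2, 4 or 9 for 3, 5 or 10 visits), against one fewer covariance parameter. Per-visit differences will be less precise than a pooled one. Baseline-by-visit terms, Kenward-Roger degrees of freedom and Day 10 as the main contrast are reasonable options, but they are preferences and the fault does not require them.

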#### **4.10 Safety Evaluation**

All safety summaries and analyses will be based upon the Safety Set as defined in [Section 4.5](#).

#### 4.10.1 Adverse Events

Adverse events will be coded using the Medical Dictionary for Regulatory Activities (MedDRA) Version 23.0 or higher.

An AE is any untoward medical occurrence in a patient or clinical study participant, temporally associated with the use of a study intervention, whether or not considered related to the study intervention.

Treatment-related AEs are those with reasonable causality to study drug marked as “related” or “possibly related” on the eCRF. AEs with an outcome of death are those with a grade of 5 or an outcome of “fatal.” AEs leading to treatment withdrawal are those with a study drug action taken of “drug withdrawn,” while AEs leading to study drug dose reduction or interruption are those with a study drug action taken of “dose reduced” or “drug interruption”, respectively.

The Investigator will make an assessment of intensity for each AE and SAE reported during the study and assign it to mild, moderate, or severe. An event is defined as ‘serious’ when it meets at least one of the predefined outcomes as described in the definition of an SAE.

An overall summary table of treatment-emergent AEs (TEAEs) will be provided with the number and percentage of patients (incidence) reporting at least one event, along with the total number of events for the following categories:

- Any AE
- AE of Grade 3 or higher
- Treatment-related AE
- Treatment-related AE of Grade 3 or higher
- Serious AE
- Treatment-related serious AE
- AE leading to death
- Treatment-related AE leading to death
- AE leading to treatment withdrawal
- Treatment-related AE leading to treatment withdrawal
- AE leading to dose reduction
- Treatment-related AE leading to dose reduction
- AE leading to dose interruption
- Treatment-related AE leading to dose interruption

Summary tables will also be presented for the incidence and total number of events by SOC and PT by treatment arm for these categories.

Counts will be by patient, not by event, and patients are only counted once within each SOC or PT. For tables categorized by maximum severity grade, patients with multiple events within a particular SOC or PT will be counted under the category of their most severe event within that SOC or PT.

A by-patient listing of all AEs will be provided. This listing will be presented by treatment arm and will include: center, patient identifier, age, gender, race, adverse event (SOC, PT, and verbatim term), date of onset, date of resolution, duration, severity, seriousness, action taken, outcome, and relatedness. The following AE listings will also be provided using a similar layout:

- Patients who died during the study
- Patients with treatment-emergent SAEs
- Patients with treatment withdrawal due to AEs
- Patients with dose reduction due to AEs
- Patients with dose interruption due to AEs

For missing or partially missing dates, imputation will be done according to [Section 4.9.1.3](#).

#### Disease Related Outcomes Not Qualifying AE/SAEs

The following disease-related events (DREs) are common in participants with COVID-19 and can be serious/life-threatening:

- Fever
- Cough\*
- Dyspnea\*
- Asthenia
- Loss of sense of taste and smell

\* *A cough or dyspnea episode related to study intervention administration does not meet the definition of a DRE and should be reported as an AE.*

Because these events are typically associated with the disease under study, they will not be reported as AEs.

NOTE: However, if either of the following conditions applies, then the event must be recorded and reported as an SAE (instead of a DRE):

- The event is, in the Investigator's opinion, of greater intensity, frequency, or duration than expected for the individual participant.

OR

- The Investigator considers that there is a reasonable possibility that the event was related to study intervention.

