#### 4.5 Analysis Sets

For purposes of analysis, the following analysis sets are defined:

- The intent-to-treat (ITT) population will include all randomized participants. The ITT participants will be analyzed according to randomized treatment, irrespective of the actual treatment received. Participants who withdraw from treatment early will be followed for the assessment of the Day 14 primary endpoint. All efficacy analyses will be performed using the ITT Population.

- The per-protocol (PP) population will include all participants in the ITT Population with no major protocol deviations that may significantly impact data integrity or patient safety. The PP Population will be used for supportive analyses of the efficacy measurements.
- The safety (SP) population will include all randomized participants who inhale any amount of study intervention or are randomized to the control arm. The SP will be analyzed according to the actual treatment received. The SP will be analyzed according to the actual treatment received. This set will be used for the safety analyses.

The efficacy summaries and analyses will be based on the ITT population. In the event that a patient is allocated the incorrect study treatment as per the study randomization list, patients will be summarized and analyzed 'as randomized' (i.e. by randomized treatment arm). In the event that a patient is stratified incorrectly, 'randomized stratum' will be used rather than 'actual stratum'. The PP Population will be used to demonstrate robustness of results for the primary efficacy endpoint

The safety summaries and analyses will be based on the SP population. In the event that a patient is allocated the incorrect study treatment as per the study randomization list, patients will be summarized and analyzed 'as treated' (i.e. by allocated treatment arm).

A by-patient listing of analysis population details will be provided. This listing will be presented by treatment arm and will include: center, patient identifier, inclusion/exclusion flag for each population, and reason for exclusion from each population.

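### By-arm AE tables are not like-for-like for cough and dyspnea, and the SAP's rule for related events conflicts with its own definition of serious

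*SAP*

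**What the plan says.** All references are to SAP version 2.0. Version 1.0, in the same file, has the same DRE rule and plans no DRE output either.

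- **Default rule (4.10.1, Disease Related Outcomes Not Qualifying AE/SAEs).** Fever, cough, dyspnea, asthenia and loss of taste and smell are DREs: "Because these events are typically associated with the disease under study, they will not be reported as AEs".
- **Footnote to cough and dyspnea.** An episode related to administration of study intervention "does not meet the definition of a DRE and should be reported as an AE".
- **NOTE.** If either of two conditions holds, "then the event must be recorded and reported as an SAE (instead of a DRE". The first condition is that the Investigator thinks the event more intense, frequent or prolonged than expected. The second is: "The Investigator considers that there is a reasonable possibility that the event was related to study intervention".
- **Seriousness (4.10.1).** An event is serious "when it meets at least one of the predefined outcomes as described in the definition of an SAE".
- **Outputs (4.10.1).** After the overall AE table, "Summary tables will also be presented for the incidence and total number of events by SOC and PT by treatment arm for these categories". For listings, "A by-patient listing of all AEs will be provided", plus listings of deaths, SAEs and AE-driven withdrawal, reduction and interruption.
- **Safety population (4.5).** It comprises "all randomized participants who inhale any amount of study intervention or are randomized to the control arm".
- **Design (1 and 3.1).** The study is open-label, and Control receives standard of care with no nebulized comparator.

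**The concern.** Section 4.10.1 defines an AE without regard to relatedness. For these five terms, however, relatedness is one of the conditions for entering the AE data. A Control patient inhales no study intervention, so a Control cough cannot practically be judged related to it. The Investigator making the judgement knows the arm. Two patients with the same cough can therefore be handled differently: one appears in the RESP301 column, and the other stays a DRE that no planned table or listing shows.

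Cough and dyspnea are plausible harms of a product nebulized three times a day, and tolerability of nebulization is a stated secondary objective. A reader of the AE tables would naturally compare the arms on these terms, and the comparison could mislead in either direction.

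The footnote and the NOTE also disagree on whether a related cough or dyspnea is an AE or an SAE. The NOTE makes events SAEs without reference to the outcome criteria. Where it does so through relatedness, non-serious events would enter the serious rows on RESP301 only.

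**Working it through.** The SAP states no figure on this point, so there is nothing to reproduce. The check has two parts: the text, then an illustration on assumed rates.

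**Text check, entry to the AE/SAE tables**

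| Route | Rule | RESP301 | Control | Reported as |
|---|---|---|---|---|
| Worse than expected | NOTE, first condition | possible | possible | SAE |
| Related to intervention | NOTE, second condition | possible | not in practice | SAE |
| Cough or dyspnea related to administration | footnote | possible | not in practice | AE |
| None of these | default | DRE | DRE | no output in 4.10–4.10.5 |

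That Control cannot use the relatedness routes is an inference from Sections 1 and 4.5; the SAP does not say it outright. The worse-than-expected route is open to both arms but is also an unblinded opinion.

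**Illustration (all rates assumed)**

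Let pT and pC be the true incidence on RESP301 and Control, g the share judged worse than expected (taken as equal in both arms), and a the share of the remaining RESP301 events attributed to the drug.

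- Table rate on Control = pC·g
- Table rate on RESP301 = pT·[g + (1−g)·a]
- Table difference minus true difference = (1−g)·[pT·a − (pT−pC)]

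*Equal true rates.* With pT = pC = 30% and g = 5%, Control shows 0.30 × 0.05 = 1.5%. RESP301 shows:
- a = 10%: 0.30 × (0.05 + 0.95 × 0.10) = 4.35%
- a = 30%: 0.30 × (0.05 + 0.95 × 0.30) = 10.05%
- a = 50%: 0.30 × (0.05 + 0.95 × 0.50) = 15.75%

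*True excess, none attributed.* With pT = 45%, pC = 30%, g = 5% and a = 0, the tables show 2.25% vs 1.5%. Events staying as DREs are 0.95 × 45% = 42.75% vs 0.95 × 30% = 28.5%, and these appear in no planned output.

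*True benefit, none attributed.* With pT = 20%, pC = 30%, g = 10% and a = 0, the table difference is 0.20 × 0.10 − 0.30 × 0.10 = −1 point, against a true −10.

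*Sensitivity to attribution.* A change of 0.10 in a moves the table difference by (1−g)·pT·0.10:

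| pT | g = 5% | g = 10% | g = 25% |
|---|---|---|---|
| 20% | 1.9 points | 1.8 | 1.5 |
| 30% | 2.85 points | 2.7 | 2.25 |

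**Precision of an attribution-free table.** The 95% half-width is 1.96·√[p(1−p)(1/n1 + 1/n2)]. At p = 20% it is:
- 40 vs 20 (first interim): 21.5 points
- 100 vs 50 (second interim): 13.6 points
- 200 vs 100 (300 randomized 2:1): 1.96 × √(0.16 × 0.015) = 9.6 points

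**The case against.** **The reporting rule belongs to the protocol.** Setting expected disease symptoms aside may well be a protocol rule. A reader might infer that doing so is itself an error; the SAP gives no ground for that. The fault is narrower: the resulting tables are presented by arm with nothing to show what was left out.

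**Other documents may fill the gap.** Section 4.12 points to a SAP Addendum and 4.10.5 to an IDMC Charter; neither is shown, nor are the protocol and eCRF. It would be too strong to say that DREs appear in no output of the trial. The statement holds for this SAP only.

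**Other outputs cover part of the harm.** Section 3.3.2 lists intolerance of nebulization and bronchial hyper-responsiveness related to nebulization. Both are tied to nebulization and give no Control comparison. NEWS 2, SpO2, the WHO scale and rescue bronchodilator use capture serious deterioration but do not count cough or dyspnea. Fever is adequately covered by temperature in NEWS 2 and vital signs, so the point rests on cough and dyspnea.

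**Accurate attribution would cure it.** A reader might infer that the bias is then zero. That requires the RESP301 rate to be at least the Control rate. If RESP301 reduces symptoms, no attribution share can bring the bias to zero, as the −1 against −10 example shows.

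**The AE/SAE conflict can be reconciled.** The footnote takes administration-related cough and dyspnea out of the DRE class, so the NOTE could be read as covering only what remains. That eases the clash between footnote and NOTE. It does not explain why the NOTE assigns SAE status without the outcome criteria that 4.10.1 requires.

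**An extra table would resolve little.** This is correct as regards testing: the half-width of about 10 points at full size exceeds most of the illustrated shifts. The table would be descriptive. Symptoms present at entry and open-label recording would still limit it.

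**Conclusion.** The point holds, as a minor one, for this SAP as shown. For cough and dyspnea the by-arm AE tables are not like-for-like, because one entry route is an unblinded relatedness judgement that can practically arise only on RESP301 and the remaining DREs have no planned output. The seriousness rule in the NOTE also contradicts the outcome-based definition in the same section.

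The size and direction of the distortion are unknown. The figures of 1.5 to 2.9 points per 10 points of attribution assume 20–30% incidence on RESP301 and 5–25% judged worse than expected; none of these comes from the SAP. A reader might infer that the tables will overstate harm on RESP301, or will hide it. The document supports neither, since over-attribution and under-attribution push in opposite directions. The primary efficacy analysis and its error rate are not affected.

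**What to change.** 1. **Correct the NOTE.** A related or worse-than-expected event is reported as an AE, and as an SAE only if it meets the outcome criteria for seriousness. This removes the conflict with the footnote and keeps non-serious related events out of the serious rows.
2. **If DREs are captured in both arms,** add to 4.10.1 one descriptive Safety Population table by arm, with a by-patient listing. It gives patients with cough and patients with dyspnea recorded as DRE, AE or SAE at any time after randomization, regardless of attribution, with the split by record type. Counting from randomization is needed because Control has no first dose. Do not restrict it to new onset, which would let attribution back in for symptoms present at entry. State that entry symptoms and open-label recording still limit the comparison. Asthenia and loss of taste and smell are optional; fever is not needed.
3. **If DREs are not captured,** state in the SAP that the AE tables for these terms are not comparable between arms.

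The cost is a wording change plus either one table and listing or one limitation sentence. The NOTE's phrase about recording an SAE in place of a DRE suggests that DREs are recorded, but the eCRF is not shown. The downsides are high background counts, wide intervals (about 10 points half-width at 20% incidence with 200 vs 100), and a start date that differs from the SAP's first-dose convention.

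### The note on disease-related events makes non-serious events SAEs in both arms, with a further inflation possible only in the RESP301 arm

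*SAP*

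**What the plan says.** All references are to SAP version 2.0. Version 1.0 has the same subsection on disease-related events.

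- **Seriousness (4.10.1).** An event is serious "when it meets at least one of the predefined outcomes as described in the definition of an SAE". The investigator separately grades each AE and SAE as mild, moderate or severe.
- **Default for the listed events (4.10.1, Disease Related Outcomes Not Qualifying AE/SAEs).** Five disease-related events (DREs) are named: fever, cough, dyspnea, asthenia and loss of taste and smell. "Because these events are typically associated with the disease under study, they will not be reported as AEs".
- **Footnote, attached to cough and dyspnea only.** "A cough or dyspnea episode related to study intervention administration does not meet the definition of a DRE and should be reported as an AE".
- **Note, covering all five.** If either of two conditions is met, "then the event must be recorded and reported as an SAE (instead of a DRE"). The first condition is that the event is, in the investigator's opinion, "of greater intensity, frequency, or duration than expected for the individual participant". The second is: "The Investigator considers that there is a reasonable possibility that the event was related to study intervention".
- **Outputs.** The overall AE table in 4.10.1 has rows for serious AEs and for treatment-related serious AEs. Section 4.10.2 asks for both again.
- **Arms.** The trial is open-label and randomizes 300 participants 2:1. Controls receive standard of care alone (sections 1 and 3.1).

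**The concern.** The note decides whether an event is an SAE by attribution or by comparison with expectation. Section 4.10.1 decides it by outcome. A possibly related mild fever, or a cough that lasts longer than expected, would be an SAE under the note and not under the definition unless it met one of the predefined outcomes.

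Two outputs are at stake. The serious-AE row would mix genuinely serious events with non-serious symptoms. The treatment-related serious-AE row would also take in any non-serious listed symptom that the investigator thinks may be due to RESP301. These are main safety summaries for a nebulized product, and the IDMC reviews safety after 10, 20, 60 and 150 participants (section 4.10.5). One of the two conditions depends on exposure to RESP301, so the reporting rule can create a difference between arms that the drug did not cause.

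**Working it through.** The SAP states no SAE rate or other figure on this point, so there is nothing to reproduce. The check is a comparison of the rules, followed by an illustration of direction.

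**1. Where each rule sends a non-serious listed event**

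| Event | Note | Footnote | Outcome-based definition |
|---|---|---|---|
| Cough or dyspnea, related to administration | SAE | AE, not a DRE | not serious |
| Fever, asthenia, taste/smell loss, possibly related | SAE | silent | not serious |
| Any of the five, worse than expected, unrelated | SAE | silent | not serious |
| Any of the five, as expected, unrelated | not triggered: stays a DRE, not an AE | silent | not serious |

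The note conflicts with the definition in the first three rows. It conflicts with the footnote only in the first.

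**2. Which arm each condition can reach**

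The worse-than-expected condition has no arm restriction. The relatedness condition needs exposure to study intervention. The safety population in section 4.5 consists of those who inhale any study intervention plus those randomized to control, so study intervention means RESP301. Controls have no nebulized product or placebo, so in practice they cannot meet this condition.

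**3. Illustration of direction**

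Let b be the genuine SAE proportion, r the proportion with a non-serious, possibly related listed event (RESP301 only), and g the proportion with a non-serious, worse-than-expected listed event (either arm). Assuming independence:

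- RESP301: apparent SAE proportion = 1 − (1 − b)(1 − r)(1 − g)
- Control: apparent SAE proportion = 1 − (1 − b)(1 − g)

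Arm sizes follow from 300 at 2:1, which is 200 and 100. The values b = 10%, r = 2–10% and g = 2–5% are assumptions and are not in the SAP.

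| r | g | RESP301 | Control | Extra patients (RESP301 / control) | Difference, points |
|---|---|---|---|---|---|
| 2% | 0 | 11.8% | 10.0% | 3.6 / 0 | 1.8 |
| 5% | 0 | 14.5% | 10.0% | 9.0 / 0 | 4.5 |
| 10% | 0 | 19.0% | 10.0% | 18.0 / 0 | 9.0 |
| 0 | 2% | 11.8% | 11.8% | 3.6 / 1.8 | 0.0 |
| 0 | 5% | 14.5% | 14.5% | 9.0 / 4.5 | 0.0 |
| 5% | 5% | 18.8% | 14.5% | 17.6 / 4.5 | 4.3 |

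For the last row: 1 − 0.90 × 0.95 × 0.95 = 0.188 for RESP301, and 1 − 0.90 × 0.95 = 0.145 for control.

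With equal g, the worse-than-expected route raises both arms alike. The difference between arms comes from the relatedness route.

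**The case against.** **The footnote may already settle cough and dyspnea.** It says a related episode "does not meet the definition of a DRE and should be reported as an AE". The note governs what is reported instead of a DRE, so an episode already outside that category need not reach the note. This is a fair reading. It means a reader should not infer that every related cough or dyspnea becomes an SAE. It does not remove the problem: the SAP does not say which rule prevails, and fever, asthenia and taste/smell loss have no footnote.

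**The note may be meant for events that are already serious.** The subsection opens by saying that these events can be serious or life-threatening. That may be the intent, but the note does not say it. On that reading the SAP also fails to say where a related, non-serious fever or asthenia is recorded.

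**The list of seriousness outcomes is not in the SAP.** Section 4.10.1 only points to it, so the list could not be checked. However, the section describes the criteria as outcomes and assesses intensity separately. Attribution and worse-than-expected intensity do not fit that description.

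**The consequences are limited.** The AE listing shows severity, seriousness and relatedness separately, so a mild related cough would be recognisable there. The SAP attaches no decision rule to SAE counts at IDMC reviews, and the Charter is not shown. NEWS 2, SpO2 and vital signs are summarized by arm regardless of attribution. Efficacy endpoints are unaffected. All of this stands and bounds the harm, but the summary tables would still be wrong.

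**Conclusion.** The point holds as a conflict of rules. Applied as written, the note makes listed events SAEs without a seriousness outcome. That contradicts the outcome-based definition for all five terms, and the footnote for cough and dyspnea. Non-serious events can enter the SAE tables in both arms, with additional inflation in the RESP301 arm through the relatedness condition.

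A reader might infer that the SAE count is inflated in the RESP301 arm only. The SAP does not support that, because the worse-than-expected condition applies equally to controls. A reader might also want a figure for the excess, for example from an assumed rate of nebulization cough. The SAP gives nothing to anchor one, and on the footnote's reading those coughs are AEs anyway. The percentages above show direction only.

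The conclusion rests on reading the note literally and on the unseen SAE definition being outcome-based, as section 4.10.1 describes it.

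**What to change.** 1. **Wording.** Amend the note so that an event leaving the DRE category is recorded as an AE, and as an SAE only if it meets the seriousness definition in 4.10.1. Bring the footnote into line, and make the same change wherever the sentence appears in the protocol and the AE reporting instructions.
2. **Tables.** Restrict the serious-AE and treatment-related serious-AE summaries in 4.10.1 and 4.10.2 to events that meet a seriousness outcome. This step is needed because new wording does not change how sites have already recorded events: the rule dates from version 1.0 (July 2020), and version 2.0 is from January 2022. If the database does not hold the outcome met by each SAE, a medical review of the affected terms is needed before lock.
3. **Comparison by arm.** Where DREs are captured in the database, add one table of the five terms by arm, combining DRE, AE and SAE records regardless of attribution. Moving related events from SAE to AE does not by itself give a fair comparison, because unattributed episodes of expected severity remain outside the AE tables. The SAP does not say that DREs are held as analysable records, so this step is conditional.

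The cost is a few sentences, a clarification to sites, a filter on existing tables and possibly one new table. Some events will move from the SAE to the AE tables, and the report should say so.
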